## 11.3.2. Nicotine Dependence (Craving and Withdrawal) Symptoms

Nicotine Dependence (Craving and Withdrawal) Symptoms will be measured by changes in the following scales:

- The Nicotine Craving Scale weekly means will be calculated and compared between treatment and sham groups.
- The Fagerstrom Test for Nicotine Dependence (FTND) composite score (sum of component scores) will be calculated and compared between treatment and sham groups.
- The Minnesota Nicotine Withdrawal Scale (MNWS) scores for the eight individual symptoms will be calculated and statistical comparisons will be performed for each individual symptom, comparing the treatment group to the sham group. Composite withdrawal symptom scores (sum of component scores) will also be calculated and compared.
- Tobacco Craving Questionnaire (TCQ- SF) composite tobacco craving scores (sum of component scores) will also be calculated and compared between treatment and sham groups.

## 11.4. Safety Measures

All subjects will undergo the following efficacy measures.

## 11.4.1. Body Examinations

- A physical examination will be completed at Baseline, at the 6 week visit and at the 4 month follow-up visit.
- Body height, weight and vital signs will be completed at Baseline, at the 6 week, visit and at the 4 month follow-up visit.
- A urine pregnancy test will be performed in all females of childbearing age at screening.

## 11.4.2. Hearing

Subjects will be informed of the risk of permanent hearing loss if an earplug should become detached or fall out and subjects will be instructed to immediately report any loosening or detachment of an earplug during DTMS, and treatment will immediately be stopped if a subject reports or if an investigator observes that a subject's earplug has loosened or has fallen out. Treatment administrators will also be instructed to wear earplugs during the treatment. Auditory threshold testing will be performed at the Screening visit and at the end of the 6 week treatment period.

11.4.3. Transcranial Magnetic Stimulation Safety (TASS) Questionnaire A screening questionnaire for transcranial magnetic stimulation will be completed at the screening visit.

## 11.4.4. Cognitive Evaluation

Evaluation using the Mini-Mental State Exam (MMSE) and the Buschke Selective Reminding Test (BSRT) for detection of cognitive changes will be completed at Screening (MMSE only), at Baseline, and at the 6 week and 4 month follow-up visits.

## 11.4.5. Adverse Events Reporting

Subjects will be instructed to report AEs as they occur. AEs will be assessed at each study visit after informed consent has been obtained.

### 11.5. Additional Measures

All subjects will undergo the following additional measure.

11.5.1. Assessment of Motivation to Quit Smoking

Subjects will be asked a motivational question, "How likely is it that you will stay off cigarettes after treatment?" in order to assess their motivation to quit smoking at the Screening visit. The responses include "very likely," "somewhat likely," and "not likely". A response of "very likely" or "somewhat likely" will qualify the subject for inclusion into the study.

# **12. SUBJECT COMPLETION / WITHDRAWAL**

# 12.1. Completion

A subject will be considered to have completed the study if he or she completed all required assessments until the 6 week follow-up visit. Subjects who prematurely discontinue study treatment for any reason before completion of the continuation phase will not be considered to have completed the study.

# 12.2. Withdrawal from the study

A subject will be withdrawn from the study for any of the following reasons:

- Lost to follow up
- Withdrawal of consent
- Subject is not compliant with requirements of the study, including inclusion criteria and exclusion criteria
- The study is prematurely stopped or halted (e.g. clinical halt)
- The investigator believes that for safety reasons (e.g. an adverse event) it is in the best interest of the subject to stop treatment
- Subject's motor threshold cannot be located.
- Subject becomes pregnant.
- Subject has significant tremor in any limb.
- Subject experiences a seizure.
- Subject misses > 4 treatments during the daily treatment phase or > 3 consecutive treatments.

When a subject withdraws before completing the study, the reason for withdrawal will be documented on the CRF.

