### 13.4. Sample size

The preliminary clinical study evaluated the safety and efficacy of the DTMS as an aid in smoking cessation, at three weeks and at six months follow-up. The three week point prevalence quit rate was 44% in the treatment group and 13% in the sham group. The six month point prevalence quit rate was 33% in the treatment group and 9% in the sham group. Although, the three week point prevalence quit rate showed a significant improvement in the treatment group compared to the sham group, the point prevalence quit rate did not meet the standard requirement for evaluating smoking cessation, i.e., at least a 4 week continuous quit rate. Furthermore, the six month data had its limitations, including a long term time point and high drop-out rate. Therefore, we looked at the clinical results provided in support of FDA approval of other smoking cessation aids, including Zyban (Bupropion hydrochloride) and Chantix (Varenicline). The mechanism of action of Zyban which aids smoking cessation is the increase in dopamine release, which is also one of the mechanisms of action of the DTMS treatment.

The quit rates (i.e., based on abstinence from week 4 of the study through week 7) were 49% in the treatment group receiving Zyban compared to 36% in patients receiving Nicotine Replacement Therapy (NRT) and 23% in the placebo group. In two other studies, subjects treated with Chantix had an abstinence rate during weeks 9 through 12 of 44% compared to 30% in patients treated with Zyban and 17% and 18% in patients receiving placebo.

For the purpose of sample size calculation the weighted average of the quit rates for smoking cessation treatments (including Zyban, Chantix, NRT and DTMS) (38.6%) and the weighted average of the quit rates for placebo/sham (18.4%) will be used. Using the above weighted averages we can assume a placebo/sham success rate of 18%, and a minimally important difference of 20%.

The study is designed to have 80% power with a two-sided level of significance of 5% to detect to detect a difference of 20% in the CQR in the DTMS group compared to the control group, and one planned interim analyses using the Lan De-Mets alpha spending approach with a Pocock type spending function (the calculations were performed using the SAS SEQDESIGN procedure).

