### 13.5. Interim Analysis (was not performed – will be detailed in the SAP)

One (1) interim analysis is planned after 106 subjects (approximately 65% information) will complete at least the 6 week visit. The main goal of this interim analysis is to stop the study in case of success, i.e. the CQR in the DTMS group is statistically significantly higher than that in the sham arm.

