### 13.6. Randomization

A subject meeting the eligibility criteria will be equally allocated (with a 1:1 ratio) to one of the following 2 treatment groups based on a randomization scheme with blocks stratified by center:

- 1. DTMS
- 2. Sham

The randomization scheme will be prepared by the study statistician using the SAS® (version 9.3.) random number procedure. The block size will be variable and study personnel will be blinded to the randomization block size.

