# 13.9.8. Handling of missing data

If a subject missed a clinic visit but had been abstinent (i.e., a negative confirmatory test) at the clinical visits prior to and following the missing visit, and claimed abstinence throughout, that subject will be classified as abstinent. Dropouts and subjects lost to follow will be classified as non-abstinent.

Additionally, the following methods of imputation may be used for the primary endpoint as further sensitivity analyses:

- Tolerability/Imputation: Assume all subjects terminated from the study due to tolerability issues are failures. For other subjects, the outcome will be obtained from the last valid assessment.
- Last Observation Carried Forward: Most recent visit with a valid assessment will be carried forward and used for the endpoint determination for these subjects.
- Multiple Imputation: Impute endpoint data using a multiple imputation model based on sex, age, race and history of smoking at baseline, as well as endpoint data computed at each intermediate time-point for all subjects with observed data.
- Best Case Scenario: Assume all subjects with missing data in the active group are successes; Assume all subjects in the sham group with missing data are failures.
- Worst Case Scenario: Assume all subjects with missing data in the active group are failures; Assume all subjects in the sham group with missing data are successes.

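### Section 12.2 ends data collection as well as treatment, so the protocol creates avoidable missing quit outcomes, and the optional multiple-imputation check in 13.9.8 leaves out treatment arm

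*Protocol*

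**What the plan says.** Section 12.2 opens its list with "A subject will be withdrawn from the study for any of the following reasons". The list contains true losses (consent withdrawn, lost to follow-up). It also contains reasons that concern stimulation, such as a safety decision to stop treatment, and "Subject misses > 4 treatments during the daily treatment phase or > 3 consecutive treatments". Section 12.1 treats anyone who discontinues treatment early as not having completed the study. No section describes diary, cotinine or other assessments after withdrawal.

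Section 13.9.8 rules: "Dropouts and subjects lost to follow will be classified as non-abstinent". Its only bridging rule covers a missed visit with negative tests on both sides.

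The denominator for the primary endpoint is narrower than all randomized subjects. Under 13.8.1, ITT-E requires at least one post-baseline assessment and an average intensity of at least 110% of motor threshold from session 3 onwards. Section 11.1.4 places the first on-treatment assessment visit at week 2.

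Among the sensitivity analyses that may be used, 13.9.8 includes "Impute endpoint data using a multiple imputation model based on sex, age, race and history of smoking at baseline", together with endpoint data at intermediate time-points. Treatment arm is not in the list.

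**The concern.** Some subjects who stop stimulation could still keep a diary and give urine. Under 12.2 they leave the study, so their quit status is set by rule and not observed.

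For withdrawal during the daily phase the result is fixed by timing. The quit date falls 7 to 14 days after the first session, and the daily phase lasts 21 days. At most 21 − 7 = 14 days of abstinence after the quit date can then be on record, against the 28 that the endpoint needs. A subject who stops sessions but stays off cigarettes counts as a failure, or leaves ITT-E altogether if withdrawn before week 2 or below the intensity condition. If the arms differ in how often this happens, the estimated difference moves for a reason other than smoking.

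The imputation analysis is one of the planned checks on missing outcomes. Without arm in the model, both arms' missing outcomes are drawn largely from one mixed distribution, which pulls the estimate towards no difference.

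**Working it through.** **Inputs.** From 13.4: "we can assume a placebo/sham success rate of 18%, and a minimally important difference of 20" percentage points, hence 38% in the active arm; 80% power, two-sided 5%; drop-out allowance 37%; 270 randomized (135 per arm). From 13.5: one interim analysis at 106 subjects, about 65% information. Withdrawal rates by arm and quit rates after withdrawal are not in the protocol; the values below are assumptions.

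**The plan's own figure.** Fixed design, unpooled variance: n = (1.960 + 0.842)² × (0.38×0.62 + 0.18×0.82) / 0.20² = 75.2 per arm. An equal-boundary Pocock design with a look at 65% information inflates this by 1.082, to 81.4. That rounds to 82 per arm, or 164, as stated. The 18%, 38% and 20 points are therefore the planning values to carry forward.

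**Withdrawal scored as failure.** Let a fraction w of each arm be withdrawn under 12.2 and remain in ITT-E.

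- Scored as failures: 38(1−w) − 18(1−w) = 20(1−w).
- Followed, withdrawn active subjects quit at 38%: 38 − 18 = 20.
- Followed, withdrawn active subjects quit at 18%: 38(1−w) + 18w − 18 = 20(1−w).

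| w in each arm | Scored as failures | Followed, quit at 18% | Followed, quit at 38% |
|---|---|---|---|
| 10% | 34.2 − 16.2 = 18 | 36.0 − 18.0 = 18 | 20 |
| 20% | 30.4 − 14.4 = 16 | 34.0 − 18.0 = 16 | 20 |

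With equal withdrawal, follow-up recovers between nothing and the full loss.

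**Unequal withdrawal.** Take 44% in one arm and 30% in the other (mean 37%), all treated as still measurable. This is deliberately large, since part of any drop-out is true loss.

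- More from active: scored 0.56×38 − 0.70×18 = 21.28 − 12.60 = 8.7. Followed at 18%: 0.56×38 + 0.44×18 − 18 = 11.2. Followed at 38%: 20.
- More from sham: scored 0.70×38 − 0.56×18 = 26.60 − 10.08 = 16.5. Followed at 18%: 0.70×38 + 0.30×18 − 18 = 14.0. Followed at 38%: 20.
- No treatment effect, 18% in both arms: scoring alone produces 18 × 0.14 = 2.5 points, against the arm that loses more.

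**Imputation without arm.** Assume 37% missing at random, equally in both arms.

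- Uninformative intermediate data: every missing outcome is drawn at the pooled 28%. Active 0.63×38 + 0.37×28 = 34.3; sham 0.63×18 + 0.37×28 = 21.7; difference 12.6. Simulation with 135 per arm gave 12.5.
- Informative intermediate data, assumed as a marker present in 95% of eventual quitters and 25% of others, known for everyone: simulation gave 15.4.
- With arm in the model, the same simulations gave 19.8 to 19.9.
- At 20% missing, the model without arm gave 15.9 to 17.7.

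In the uninformative case the imputed difference equals the one from scoring failures, 20 × 0.63 = 12.6. Agreement between the two would look like robustness but would be built in.

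**The case against.** Scoring dropouts as non-abstinent is an explicit, deliberate rule, and observed outcomes after stopping treatment answer a somewhat different question. That stands. The criticism is that the protocol stops measuring people it could still measure, not that it has a rule for outcomes that remain missing.

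A reader might infer several stronger things that the protocol does not support:

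- *The scoring rule costs 2 points at 10% withdrawal and 4 at 20%.* Only if withdrawn active subjects still quit at 38%. At the sham rate and with equal withdrawal, following them changes nothing.
- *Anyone who misses treatment is scored a smoker.* A few missed sessions do not trigger 12.2, and early withdrawals or those below the intensity condition leave ITT-E. A subject whose motor threshold cannot be found at the start would mostly be outside the set.
- *These withdrawals come on top of the 37%.* Section 13.9.4 names adverse events and poor compliance as reasons for discontinuation, so they probably fall within it.
- *Active stimulation is less tolerable, so bias is expected.* No by-arm rates are given. Section 3.1 describes a sham that mimics the scalp sensations, and 2.4 calls treatment well tolerated. The direction of any imbalance is unknown.

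The imputation is optional. Best-case and worst-case analyses distinguish the arms, the intermediate data carry some arm information, and the bias is towards no difference. This limits the consequence. But the protocol itself fixes the variable list, and the best and worst cases are extreme bounds, not plausible estimates. The secondary quit rate and the completer set condition on having the assessments, so they do not recover withdrawn subjects' outcomes.

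**Conclusion.** The point holds in a limited form. Section 12.2 creates avoidable missing primary outcomes, which 13.9.8 sets to failure or 13.8.1 removes from the efficacy set. At 10% equal withdrawal the reported difference would be 18 points, where follow-up would show 18 to 20. The clearer risk is unequal withdrawal, which shifts the estimate either way: 2.5 points with no true effect in the 44%/30% illustration. All withdrawal rates here are assumed.

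The omission of arm biases one optional sensitivity analysis to about 12.5 to 15.4 points against a true 20, given 37% missing at random. Withdrawal in the first weeks leaves little intermediate data, so the lower end is the more relevant for those subjects. A reader might infer that the primary analysis is invalid, or that a false positive is likely; neither follows. Both weaknesses are worth correcting because correction is cheap.

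**What to change.** In 12.2, leave all stopping criteria unchanged and distinguish stopping treatment from ending data collection. For subjects who stop treatment, continue the scheduled weekly diary, cotinine and adverse event assessments to week 6. Do so where the subject consents and where sections 15.2.1 (termination from the study after an adverse event) and 15.2.3 (withdrawal on pregnancy) do not require removal. Section 12.2 must be reconciled with those two, and 12.1 worded to match. Limiting study withdrawal to consent and loss to follow-up alone would contradict them.

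Use the observed outcomes in the primary analysis, and keep the non-abstinent rule for outcomes that remain missing.

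In 13.9.8, add treatment arm to the imputation model or impute separately by arm, with baseline cigarettes per day as a further covariate.

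Cost: an amendment and at most five weekly assessments (weeks 2 to 6) for each subject who stops treatment. It brings no gain for subjects already withdrawn, and the past tense about drop-out monitoring and the interim analysis in 13.4 and 13.5 suggests there may be many. It also does not bring back subjects excluded by the intensity condition. The imputation change needs only an edit to the analysis text.

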# **13. STATISTICAL CONSIDERATIONS**

### 13.1. Study Design and Objectives

This is a prospective, randomized, 4 month, double blind, controlled trial in outpatients recruited from hospitals and clinics, using a sequential two-stage adaptive design with one interim analysis at approximately 65% of the expected information.

The aim of this study is to evaluate the safety and efficacy of DTMS compared to sham treatment as an aid to smoking cessation in chronic (>10 cigarettes/day) cigarette smokers.

### 13.2. Study Endpoints

# 13.2.1. Primary Efficacy Endpoint

The primary endpoint is the four-week continuous quit rate (CQR), representing abstinence during a consecutive 4 week period. Weekly abstinence is defined as a subject's self-report (in diary) of no smoking (0 cigarettes/day during the whole week), confirmed by urine cotinine levels  $\leq 200$  ng/ml. A missing confirmatory test will be considered negative, if the previous and the following weekly or 4 month follow-up confirmatory tests are negative. Quit rates are defined as the ratio of the number of patients meeting the quit criterion for at least 4 consecutive weeks to the number of patients initially treated and having at least one post-baseline assessment.

# 13.2.2. Secondary Efficacy Endpoints

The secondary endpoints are:

- The four-week continuous quit rate (CQR), representing abstinence during a consecutive 4 week period for subjects having assessments during a consecutive 4 weeks period, therefore the quit rates are defined as the ratio of the number of patients meeting the quit criterion for at least 4 consecutive weeks to the total number of patients having assessments during a consecutive 4 week period.
- The number of cigarettes smoked per day (per diary data) for all subjects (quitters and non-quitters).

13.2.3. Exploratory Efficacy Endpoints Additional endpoints include:

- Weekly point prevalence abstinence rates, defined as the ratio of the number of subjects meeting the weekly abstinence criterion to the number of subjects initially treated and having at least one post-baseline assessment.
- Number of cigarettes smoked per day (per diary data) for non-quitter subjects only.
- Withdrawal symptoms as measured by weekly scales measuring nicotine craving and dependence/withdrawal, including the Fagerstrom Test for Nicotine Dependence (FTND), Minnesota Nicotine Withdrawal Scale Self-Report (MNWS), Tobacco Craving Questionnaire–Short Form (TCQ-SF) and Nicotine Craving Scale.

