Given this design we will require a total number of 164 (82 per arm) subjects at most. Allowing for a potential 37% drop-out 270 subjects will be randomized. The dropout rate was continuously monitored in a blinded way, and the total number of subjects to be enrolled was adapted accordingly.

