#### 13.8.3. Statistical Analysis of Analysis Sets

The ITT-E and ITT-S analysis sets will serve as the main set for efficacy and safety assessments, respectively.

The primary efficacy assessment will also be performed on the CO and the PP analysis sets, as a sensitivity analysis.

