### 13.9.2. Significance levels and handling of type I error

The overall significance level for this study is 5% using two-tailed tests, except for the treatment by site interaction that will be tested at a significance level of 10%.

The hierarchy approach will be adopted for the primary and secondary endpoints to control the type I error due to multiple endpoint testing. Thus, the primary endpoint will first be analyzed and only if found statistically significant as detailed in section 13.4, will the first secondary endpoint be analyzed; and only if found statistically significant, will the second secondary endpoint be analyzed. This approach will maintain the overall study type I error by continuing to analyze the next end-point in the hierarchy only if the previous endpoint analysis was found significant.

The exploratory end-points will not be part of the hierarchy as descriptive statistics are mainly planned.

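### The first secondary endpoint is the primary quit rate over a denominator selected by retention, yet it sits in the alpha-controlled hierarchy and gates cigarettes per day

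*Protocol*

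**What the plan says.** Protocol 13.2.1 defines the primary CQR over subjects who were treated and have at least one post-baseline assessment. Section 13.2.2 lists two secondary endpoints. The first is the same CQR with the same quit criterion, but divided by a smaller count: the ratio is taken "to the total number of patients having assessments during a consecutive 4 week period". The synopsis and 5.2 repeat this definition. The second is cigarettes per day in all subjects.

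Section 13.9.2 puts both in a fixed sequence after the primary. The first secondary must succeed, and "only if found statistically significant, will the second secondary endpoint be analyzed".

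Two other sections bear on this. Section 13.9.8 classes dropouts and subjects lost to follow-up as not abstinent. Section 13.8.3 says of the completer (CO) and per-protocol (PP) sets: "The primary efficacy assessment will also be performed on the CO and the PP analysis sets, as a sensitivity analysis".

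**The concern.** Whether a subject has four weeks of assessments in a row is known only after randomisation and may depend on treatment and on smoking status. Dividing by that subset removes subjects whom 13.9.8 counts as failures. The protocol therefore handles dropouts in two opposite ways for the same quit criterion, and gives a completer-type quit rate a supportive role in 13.8.3 and a confirmatory one in 13.9.2.

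Two things are at stake. A claim carrying type I error control would rest on a comparison that differential retention can bias in either direction. And access to cigarettes per day, the only secondary endpoint that is not a restatement of the primary, would depend on that comparison.

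**Working it through.** **Inputs from the protocol.** Section 13.4 assumes a "placebo/sham success rate of 18%, and a minimally important difference of 20" points, so 18% against 38%, with 80% power at two-sided 5%. It states "we will require a total number of 164 (82 per arm) subjects at most", then "Allowing for a potential 37% drop-out 270 subjects will be randomized", which is 135 per arm. Section 13.4.4 tests the primary at 3.154% at the final analysis.

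**Assumptions of this check.** The secondary level is taken as 5%, since none is stated separately. No quitter is excluded from the narrower denominator. All 135 per arm count in the primary denominator. Unequal drop-out splits are assumed, each averaging the stated 37%.

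**1. The plan's own figure.** The unpooled fixed-design size is (1.960 + 0.842)² × (0.18 × 0.82 + 0.38 × 0.62) / 0.20² = 75.2 per arm. A constant two-look Pocock boundary at 65% information has a nominal level of 0.0315 and an inflation factor of 1.082. Then 75.2 × 1.082 = 81.4, so 82 per arm, as stated.

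**2. Effect on the rate.** With the same numerator, secondary rate = primary rate / (1 − d), where d is the share without four consecutive weeks of assessments.

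- If 18% and 38% apply to all treated subjects and d = 37% in both arms: 0.38/0.63 = 60.3% and 0.18/0.63 = 28.6%. The difference is 31.7 points instead of 20. At d = 20% the rates are 47.5% and 22.5%.
- If 18% and 38% were meant for evaluable subjects, the secondary rates are 38% and 18%, and the primary rates are 0.38 × 0.63 = 23.9% and 0.18 × 0.63 = 11.3%.

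On either reading, the secondary rate at d = 37% is 1/0.63 = 1.59 times the primary rate.

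**3. The gate when the device works.** On the first reading, with 135 per arm, primary power at 3.154% is about 94%. The last column comes from 400,000 simulated trials per scenario.

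| Drop-out DTMS / sham | Secondary CQR DTMS | Secondary CQR sham | Difference (points) | Passes first secondary, given positive primary |
|---|---|---|---|---|
| 37% / 37% | 60.3% | 28.6% | 31.7 | 99.9% |
| 30% / 44% | 54.3% | 32.1% | 22.1 | 87.8% |
| 27% / 47% | 52.1% | 34.0% | 18.1 | 69.7% |
| 44% / 30% | 67.9% | 25.7% | 42.1 | not simulated |
| 47% / 27% | 71.7% | 24.7% | 47.0 | not simulated |

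The true primary difference is 20 points in every row. With 30% / 44% drop-out, 100 − 87.8 = about 12% of trials with a positive primary are barred from testing cigarettes per day. With 27% / 47% it is about 30%. The last two rows show the opposite bias, in favour of the device.

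**4. No treatment effect (18% in both arms).** Taken alone at 5%, the secondary test rejects in 5.1% of trials at 37% / 37%, 10.2% at 42% / 32%, 15.4% at 44% / 30% and 26.7% at 47% / 27%. In the sequence of 13.9.2 it is reached only after a significant primary. At 44% / 30%, both tests reject in about 1.8% of trials.

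**The case against.** A reader might infer that the trial's false-positive rate rises to 15% or more. The protocol does not support that. Those figures are for the secondary test standing alone, and 13.9.2 forbids the test unless the primary has succeeded. Familywise error under the global null is not inflated.

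A reader might also infer that the smaller sample makes the endpoint likely to fail. With equal drop-out the opposite holds: the numerator is kept, the difference widens, and power is about 99% against 94% for the primary. Blocking needs clearly higher drop-out on sham, and the protocol gives only one overall figure of 37%.

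Nor is this the same comparison as the planned CO analysis. The CO set requires membership of the efficacy ITT set and six weeks of treatment and assessments. This denominator needs only four consecutive weeks, so with visits at weeks 2 to 6 a subject who leaves after week 5 stays in. The two sets overlap but are not identical, and 37% drop-out need not mean 37% excluded.

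Finally, the primary denominator and the efficacy ITT set also use post-randomisation conditions, so the difference is one of degree. The primary does, however, keep as failures the dropouts who have a post-baseline assessment, and this endpoint removes those without the four weeks.

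All of these limits stand. They narrow the harm. They do not explain why a retention-selected rate should be confirmatory, or why it should precede a comparison in all subjects.

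**Conclusion.** The point holds in a limited form. The first secondary is the primary CQR over a subset selected after randomisation. It conflicts with the protocol's own dropout rule and with the sensitivity role given to a similar analysis. As long as every quitter stays in the denominator, its rate cannot be lower than the primary rate; at 37% excluded it is 1.59 times as high. The figures of 60% and 29% assume that the planning rates apply to all treated subjects, which the protocol does not settle.

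The gate does harm only when drop-out is unequal. It costs almost nothing at equal drop-out and blocks cigarettes per day in about 12% or 30% of primary-positive trials under the two assumed splits with more sham drop-out. More DTMS drop-out flatters the device. These percentages rest on 38% against 18% in all treated subjects, 135 per arm and a 5% secondary level. The primary analysis and its error rate are untouched, so this is an inexpensive improvement and does not threaten the trial's main conclusion.

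**What to change.** Before unblinding, take this CQR out of the hierarchy in 13.9.2 and report it as a sensitivity analysis beside the CO analysis. Test cigarettes per day in all subjects directly after the primary. Change the wording to match in the synopsis, 5.2 and 13.2.2.

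No visit, measurement or sample size changes, and the rate can still be reported. The sponsor gives up a confirmatory claim on the observed-case rate. The past tense used for drop-out monitoring in 13.4 and for the interim in the heading of 13.5 suggests the trial was already running. Reordering a pre-specified sequence therefore needs a documented amendment, dated before anyone sees results by arm.
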